6.4 OUTCOME ASSESSMENT SCHEDULE

An overview of the outcome assessment schedule is given in **Table 2**.

Free sugar intakes and adherence will be assessed throughout the intervention period as given in **Table 1**. All other outcomes will be assessed at baseline and at trial end, with the exception of the following: sweet liker status, PROP taste sensitivity and demographic characteristics will be measured only at baseline; questions on adherence and difficulties will be asked at weeks 4, 8 and 12.

All participants will undertake all measures, in the same manner, regardless of intervention arm. Dietary assessments, questions on adherence and difficulties will be undertaken via the Nutritics software. Self-report questionnaires will be administered online via Qualtrics. Measures associated with taste status and appetite will be presented to participants using a paper format to be completed during a test session.

Compliance with trial measures will be enhanced using a bogus pipeline method (Hugh, 2013; Muhlheim et al., 1997; Reid et al., 2014); participants will be asked to provide a saliva sample at baseline and at trial end, for the supposed purpose of examining salivary enzymes that may vary with dietary change. In reality, samples will be discarded. Only at the end of the trial will participants be informed that their samples have not been analysed.

Table 2: Schedule of enrolment, interventions and assessments

	Trial period						
	Enrolment	Baseline	Intervention			End	
Time point	Wk -1 / 2	0	Wk 1	Wk 2	Wk 4	Wk 8	Wk 12
Enrolment							
Eligibility screen	X						
Informed consent	X						
Allocation		X					
Intervention							
Intervention groups							→
Control group							→
Assessments							
24hr diet diary							→
3 day diaries	X	X					X
Adherence							→
Adherence questions					X	X	X
Anthropometrics		X					X

Sweet liker status		X					
PROP taste test		X					
Sweet taste test		X					X
Sweet food choice		X					X
Sweet attitudes		X					X
TFEQ		X					X
FCQ		X					X
Demographics		X					
Knowledge		X					X
GSLTPAQ		X					X
SF36		X					X
Adverse events							→
Difficulties / Adverse events					X	X	X
Interview			X*	X*	X*	X*	X*
BP cheek swab	X						X

X* Interviews completed only once. TFEQ: Three-factor eating questionnaire; FCQ: Food choice questionnaire; GSLTPAQ: Godin- Shepard leisure time physical activity questionnaire; SF-36: Short-form 36 measure of quality of life; BP: Bogus pipeline method.

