8.1 ANALYSES ONE: EFFECTS OF THE DIFFERENT DIETARY RECOMMENDATIONS

To test the effects of the different dietary recommendations, a series of multiple regression analyses will be run. A separate analysis will be run for each outcome variable, where the outcome at week 12 will be predicted by trial arm (intervention/control) and outcome variable at baseline. Additional independent variables will also be included in each analysis as possible, to include: demographic variables, total energy intakes, sweet liker status; PROP taster status; and attitudes to sweet foods, eating behaviour and food choice.

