Primary models will include gender, age, control/intervention group, baseline %FS, baseline body weight (as randomization variables), and baseline variable of interest. In analyses for %FS, sugar-sweetened food intake, LCS-sweetened food intake, body weight and waist circumference, TEI at Week 12 and physical activity at Week 12 will also be included. Secondary models will also include any additional variable that correlates with each outcome when assessed independently. All variables measured will be considered as secondary variables. Effects for all continuous variables will be investigated using linear multiple regression. Effects for adherence will be investigated using logistic regression to predict adherent vs not adherent.

Analyses Two: Quantitative Data

For analyses two, analyses one will be repeated for demographic groups where significant associations for these variables were found in analyses one. Analyses will only be conducted if significant associations are reported. If no significant associations with demographic variables are found, these analyses will not be completed. These analyses are intended to demonstrate differing effects of the intervention/s in different population groups.

Analyses Three: Qualitative Data

Analyses three will investigate the qualitative data collected from a subset of participants using solo interviews. These interviews were scheduled for completion in a sample of 80 participants from different intervention groups and at different time points. These analyses will be undertaken using a thematic framework analysis. First, a random sample of interviews will be analysed inductively using thematic analysis to identify codes. These codes will be used to create a framework and the framework then applied to all interviews.

Framework analysis has been chosen as a suitable analytical method for evaluating the qualitative interview data gathered, due to an interest in individual experiences and seeks to identify the different factors (barriers or facilitators) that contributed to successful or unsuccessful dietary change (Braun & Clark, 2013). The practical methods for conducting framework analysis follow a methodology as outlined below.

Framework analysis (Braun & Clarke, 2006; 2013; Gale et al, 2013).

Phase 1 'Familiarizing yourself: Transcribing data (if necessary), reading and re-reading the data, noting down with your data: initial ideas'.

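### The secondary models admit any measured correlate of the outcome, with no limit to pre-allocation measurements, so week-12 variables that the advice changes can enter and remove part or all of the arm effect

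*SAP*

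**What the plan says.** The SAP (Analyses One: Quantitative Data) sets out two layers of model. For the first: "Primary models will include gender, age, control/intervention group, baseline %FS, baseline body weight (as randomization variables), and baseline variable of interest". For %FS, the two sweetened-food intakes, body weight and waist circumference it adds that "TEI at Week 12 and physical activity at Week 12 will also be included". The second layer, the secondary models, adds to this and defines the candidate pool: "any additional variable that correlates with each outcome when assessed independently. All variables measured will be considered as secondary variables". No entry threshold is given for the correlation, no time point for the candidates, and no exclusion for variables that allocation may affect.

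Protocol 6.4 says of everything apart from free sugar intake and adherence, with a few stated exceptions, that "All other outcomes will be assessed at baseline and at trial end". Most candidates therefore exist in a baseline and a week-12 version. Protocol 8.1 names additional covariates, among them demographic variables, total energy intake, "sweet liker status; PROP taster status; and attitudes to sweet foods, eating behaviour and food choice", but does not say at which time they are measured.

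The only screen on regression variables is in the SAP under Data presentation: a multicollinearity check with a correlation cut-off of 0.7.

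**The concern.** Randomisation makes the arms comparable on everything measured before allocation. It gives no such protection to a comparison made at equal values of something measured afterwards. The advice in groups NF and NFS asks people to eat fewer high-sugar foods, and in NFS to use low-sugar versions (Protocol 5.1.2 and 5.1.3). Protocol 5.1.5 says that low-calorie sweetener use and information gathering will be assessed as outcomes. Week-12 sweet-food counts, sweetener use, knowledge and attitudes are thus among the routes by which the advice might work. A model that holds them fixed asks what the advice does other than through those routes, which is not the trial's question.

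Some candidates are closer still. %FS is energy from free sugars divided by total energy. Week-12 total energy is already in the primary %FS model. If week-12 free sugars in grams joins it, the model comes close to rebuilding the outcome from its own parts, and little is left for the arm term to explain.

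At stake is how the secondary models are read. An arm coefficient that shrinks after such adjustment could be reported as showing that the advice has little effect once other factors are considered, when the adjustment itself caused the shrinkage.

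**Working it through.** **Inputs from the documents.** Effect 2 percentage points of TEI and standardised difference 0.8 (Protocol 4.2), so SD = 2/0.8 = 2.5. There are 60 per arm with 20% attrition, so 60 × 0.8 = 48 completers per arm. Alpha is 0.05, taken as two-sided. N = 242 (SAP, Data presentation).

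**The plan's own figure.** The standard formula gives 2 × (1.96 + 0.84)² / 0.8² = 24.5, so 25 per arm, and 25/0.8 = 31.25, so 32 after attrition. The stated 60 per arm is not reproduced. The trial is larger than its inputs require, which has no bearing on this point; only the 2 points, the SD and the 48 completers are used below. Unadjusted power at 48 per arm is 0.975.

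**How easily a variable enters.** Taking p<0.05 as the entry rule (an assumption), the critical correlation at N = 242 is t/√(t² + 240) with t = 1.97, about 0.126. Weak correlates qualify.

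**One added week-12 variable.** Let dM be the arm shift in that variable in SD units, in the direction that accompanies lower %FS. Let r be its within-arm correlation with week-12 %FS. The documents give neither. SD 2.5 is taken as the within-arm SD of week-12 %FS, and one advice arm is compared with control.

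- Adjusted arm effect = 2 − r × 2.5 × dM
- Standard error = 2.5 × √(1 − r²) × √(1 + dM²/4) × √(2/48)

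| dM | r | Adjusted effect (points) | Removed | Power |
|---|---|---|---|---|
| 0 | 0.5 | 2.00 | 0% | 0.99 |
| 0.2 | 0.3 | 2 − 0.15 = 1.85 | 7.5% | 0.97 |
| 0.4 | 0.5 | 2 − 0.50 = 1.50 | 25% | 0.91 |
| 0.8 | 0.5 | 2 − 1.00 = 1.00 | 50% | 0.56 |
| 1.0 | 0.8 | 2 − 2.00 = 0.00 | 100% | 0.03 |

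Simulation (2,000 runs, 48 per arm, entry at p<0.05) agreed: 1.49 points and power 0.90 in the third row, 0.99 points and power 0.54 in the fourth.

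**Three such variables.** With r = 0.5 each and correlations of 0.3 among them (assumed), the coefficients in SD units sum to 3 × 0.5/(1 + 2 × 0.3) = 0.9375. The adjusted effect is 2 − 2.5 × 0.4 × 0.9375 = 1.06 at dM 0.4, and 2 − 2.5 × 0.8 × 0.9375 = 0.13 at dM 0.8. Simulation gave 1.05 points (power 0.76) and 0.13 points (power 0.07).

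**Same entry rule, baseline candidates only.** The simulated mean arm effect stays at 1.98 to 2.01 points, with power 0.99 to 1.00. The damage comes from when the variable is measured, not from selecting by correlation.

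**The 0.7 check.** Applied between a candidate and the arm, the correlation is (dM/2)/√(1 + dM²/4): 0.10 at dM 0.2, 0.20 at 0.4, 0.37 at 0.8 and 0.45 at 1.0. All are well under 0.7, so a variable that the advice changes passes. The check may keep out near-duplicates among the covariates, such as total and free sugars, but it does not ask whether a variable was affected by allocation.

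**The case against.** The strongest reply is that the secondary rule names no time point, whereas the SAP does name week 12 when it wants a week-12 covariate. On that view the text is incomplete and is not a plan to adjust for consequences of the advice. It is fair that nowhere does the SAP state that week-12 sugars, counts or attitudes will enter, and no data show which correlates are strongest. But the rule is not silent about its pool: it takes in everything measured. The same paragraph already uses week-12 covariates, so followed as written the rule admits them.

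Several stronger readings are tempting and are not supported:

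- That the arm effect will be adjusted away. The loss runs from none to all, depending on dM and r. A shift as large as 0.8 SD in attitudes or knowledge has no basis in the documents, and a variable that the advice does not move removes nothing.
- That selection by correlation in itself biases the arm effect. Among baseline variables it leaves the effect essentially unchanged.
- That the SAP discards a closed protocol list. Protocol 8.1 is open-ended and gives no timing, and Protocol 8.2 already expects further variables to be identified from the first analyses.
- That this search decides the subgroup analyses. Under Analyses Two, "analyses one will be repeated for demographic groups where significant associations for these variables were found in analyses one"; this is confined to demographics, and gender and age are already in the primary models.
- That the primary results are compromised by this rule. They are not. The week-12 energy and activity terms in those models are a related but separate point, although they mean that the primary %FS model is not a clean fallback.

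**Conclusion.** The point holds for the secondary models. As written, their entry rule admits week-12 variables that are parts of the outcome or are targeted by the advice, and nothing elsewhere in the documents, including the 0.7 check, keeps them out. The consequence is partial or complete loss of the arm effect in those models. Across the combinations tabulated for one added variable, the loss runs from 0% to 100% of a 2-point effect, with 25% at moderate values (dM 0.4, r 0.5), and it is larger if several enter. These figures rest on assumed values of dM and r, a linear model and the planning SD of 2.5; they are illustrations, not predictions. The change should be made, but the rule does not touch the primary arm contrasts.

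**What to change.** In every model used to estimate the arm effect, restrict additional covariates to variables measured before allocation and named in advance. Draw them from the Protocol 8.1 list at baseline values: demographics, total energy intake, sweet liker status, PROP status, and attitudes to sweet foods, eating behaviour and food choice.

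Include sweet liker and PROP status only where data allow, or state how missing values are handled. At-home participants skip the solution-based sweet liker measure (Protocol 7.3), and neither variable appears in the SAP's listed imputation sequence.

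Report any model containing week-12 variables separately, labelled as exploratory association or mediation, and draw no conclusion about the arm effect from it.

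The cost is SAP wording plus a short rule for missing taste-status data, which may touch the imputation plan. What is given up is the search for unlisted correlates within the arm-effect models; that search can still be done in the exploratory models.

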8.2 ANALYSES TWO: EFFECTS IN DIFFERENT POPULATION SUBGROUPS

The above analyses will be repeated in specific population groups, assuming appropriate numbers, based on demographic variables and other variables identified as important in analyses one.

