This updated data from CSV2 was copied into a new file named CSV4. In CSV4 a helper column combining the participants ID number and log day (eg: JS19900.1, combination of JS1990 and 0.1) was used in combination with a new sheet to summarise all nutrients for each participant and each diet diary day. This resulted in 5120 unique daily totals across all nutrients. The CSV4 file was then saved as complete. Including all participants and screened non-participants a total of 70747 individual diary entries on the study via Nutritics Libro. Of these data, 67546 were participant entries and 3201 from non-participant screening diaries, with a total of 10757 unique food items logged.

Sweetener and sweet food counts

Foods that contained sweeteners, were high, medium or low in sugar were separated into counts for each diet diary. These counts were then added into 5 separate scores for the summation of foods consumed in each category for baseline, timepoints 1-4 and endpoint.

ALL DATA - MULTIPLE IMPUTATION

Main analyses were completed on an intention to treat basis as the gold standard for representing the applicability of the intervention in a real world setting rather than an ideal outcome. A variety of techniques to replace/analyse RCT results with missing data have been previously utilised including complete case analysis (CCA), single imputation (SI)(by last observation carried forward, mean or regression), multiple imputation or mixed-effect models (Bell et al., 2014; Li & Stuart, 2019; Ren et al., 2022). CCA and SI methods were discounted due to CCA not being reflective of real-world data, reducing statistical power and SI lacking uncertainty and most likely underestimating variance.

Instructions for the steps used to complete MI and the imputation sequence are included below. As multiple imputation is completed in the order of the variables within the analysis, the variables list was set as randomisation variables first, then nutrient values, anthropometrics and finally questionnaire data in the order that they were completed. All baseline variables were used as predictors, all endpoint variables used as imputations only due to the monotonic pattern.

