Three distinct analyses were pre-specified in advance: 1) Analyses of the population as a whole to investigate the effects of the three different types of dietary recommendation versus control; 2) Analyses of the effects of the dietary recommendations in different population subgroups, and 3) Investigation of the barriers and facilitators to success.

Data presentation

Data will be presented as mean \pm standard deviation in all cases, unless stated. Values will be considered significant at the $p<0.05$ level. Before completing analyses, data will be checked for normality. The data set is large, $N=242$, thus a normal distribution will be assumed. Where assumptions of homogeneity of variance are violated (Levene's test $p<0.05$), statistics will be taken from analyses conducted assuming non-equal variances. Bonferroni corrections for multiple testing will be applied to data where tests were not pre-specified in the study protocol. Where multiple regression analyses are used, all variables will be checked for multicollinearity using correlation cut-offs of <0.7 . Pearson correlation values will be used for all continuous variables, and Spearman correlations for categorical variables.

Participant characteristics

Details of study completion will be provided and a CONSORT diagram created detailing number randomized to each group, number completing the study in each group, drop out and number included in all analyses.

Characteristics will be given for the whole sample and for each trial group.

Analyses One: Quantitative Data

For analyses one, multiple regression analyses will be used. Analyses will be conducted for both primary outcomes, for key secondary outcomes - daily energy intake, sugar-sweetened food intake, LCS-sweetened food intake, body weight, waist circumference, and adverse events; and change (baseline - week 12) data for these outcomes; and for other secondary outcomes (dietary

composition, sweet food perceptions and preferences, sweet food choice, attitudes to sweet foods, attitudes towards eating behaviour, motives for food choice, knowledge and lifestyle variables, quality of life) if differences are found in the sample as a whole from baseline to week 12. This will reduce the number of exploratory tests undertaken. Differences from baseline to week 12 will be investigated by paired t-tests. Primary outcomes and outcomes associated with dietary composition will also be investigated in the same manner at weeks 1, 2, 4 and 8.

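### Analyses Two is meant to show differing intervention effects, but a demographic main effect opens it and no test of the difference between groups is stated

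*SAP*

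**What the plan says.** SAP, Analyses Two: Quantitative Data, gives three rules.

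- Aim: "These analyses are intended to demonstrate differing effects of the intervention/s in different population groups".
- Trigger: "analyses one will be repeated for demographic groups where significant associations for these variables were found in analyses one".
- Closure: "If no significant associations with demographic variables are found, these analyses will not be completed".

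The associations come from the models under Analyses One: Quantitative Data. There, "Primary models will include gender, age, control/intervention group, baseline %FS, baseline body weight (as randomization variables), and baseline variable of interest". Some outcomes also take week 12 energy intake and physical activity. Then "Secondary models will also include any additional variable that correlates with each outcome when assessed independently". No product of arm with another variable is listed.

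Protocol 8.2 repeats the analyses in population groups, if numbers allow, "based on demographic variables and other variables identified as important in analyses one". It states no comparison between groups either.

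On multiplicity, SAP, Data presentation, says "Bonferroni corrections for multiple testing will be applied to data where tests were not pre-specified in the study protocol".

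**The concern.** A significant coefficient for gender or age in a main-effects model says that the outcome differs by gender or age, averaged over arms. Whether a recommendation works better in one group is a separate question. The trigger is therefore neither necessary nor sufficient for what Analyses Two sets out to show.

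Once triggered, the plan yields one set of arm coefficients per group and no stated way to judge whether they differ. Two errors can follow. A result significant in one group only may be taken as a differing effect when the true effects are equal. A real difference may never be examined because the variable has no clear overall association with the outcome. Analyses Two is one of the three analyses that both documents set out in advance, and the SAP does not label it exploratory.

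**Working it through.** The documents give no figure for Analyses Two, so there is none to reproduce. The numbers below only illustrate size.

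**Inputs.** From protocol 4.2: 60 per arm, 20% attrition, standardised difference 0.8. From SAP, Data presentation: significance at 0.05, taken as two-sided. Assumed: SD 1, two equal groups, and *h* people per arm per group. With everyone analysed, *h* = 60/2 = 30, which is closest to the plan ("Main analyses were completed on an intention to treat basis"). With 20% lost, *h* = 60 × 0.8/2 = 24. Ranges below run over these two values.

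**1. Equal true effects, groups fitted separately.** Let *p* be the power of the arm-versus-control t-test in one group. The chance of significance in exactly one group is 2*p*(1 − *p*). Adjusting for a baseline that correlates *r* with the outcome divides the effect by √(1 − *r*²); at *r* = 0.5 it becomes 0.8/√0.75 = 0.924.

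| Arm coding | r | p (h = 24 / 30) | One group only (h = 24 / 30) |
|---|---|---|---|
| One arm v control, h v h | 0 | 0.774 / 0.861 | 0.350 / 0.239 |
| One arm v control, h v h | 0.5 | 0.880 / 0.940 | 0.212 / 0.112 |
| Any intervention v control, 3h v h | 0 | 0.919 / 0.964 | 0.149 / 0.069 |
| Any intervention v control, 3h v h | 0.5 | 0.972 / 0.991 | 0.053 / 0.017 |

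For example, 2 × 0.774 × 0.226 = 0.350. A 3-df arm-by-group interaction test in the full sample was falsely positive in about 5% of simulated trials.

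**2. Adding the gate.** The figures in step 1 apply once the analysis is run. In a 12,000-run simulation (four arm levels, unadjusted), the chance that the gate opens and one contrast is significant in one group only depends on how strongly the demographic variable predicts the outcome:

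| Prognostic effect (SD) | 0 | 0.1 | 0.2 | 0.3 | 0.5 |
|---|---|---|---|---|---|
| Gate opens and results disagree | 1–2% | 3–4% | 8–10% | 15–18% | 23–32% |

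The excess over 5% is thus large only for a fairly strong predictor.

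**3. A real difference in one arm and one group (0.8 SD).**
- Gate: averaged over four arms, the group main effect is 0.8/4 = 0.2 SD. Its standard error is √(4/N) with N = 8*h* = 192 or 240, that is 0.144 or 0.129. The ratios are 1.39 and 1.55, and the gate opens in about 28% or 34%. Allowing for the residual variance added by the omitted interaction gives 27% or 33%; simulation gives 27.5% or 33.8%.
- Interaction: the noncentrality is (*h*/2) × Σ(δ − mean δ)² with δ = (0, 0, 0, 0.8). The sum is 0.64 − 4 × 0.04 = 0.48, so the noncentrality is 5.76 or 7.20. Power of the 3-df test is 0.491 or 0.595.

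**4. All three arms work in one group only.** The main effect is 3 × 0.8/4 = 0.6 SD. The gate opens in 98.5% or 99.6%, so little is lost.

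**5. Extremes that separate the two questions.** A variable with a 0.5 SD prognostic effect and no effect modification opens the gate in 93–97% of trials. A 0.8 SD effect difference arranged to leave no net association opens it in 4–5%, while the interaction test detects it in 50–60%.

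**The case against.** **The SAP never says that significance patterns will be compared.** This is correct. A reader might infer that a differing effect will be declared from one significant and one non-significant group. The text does not say so, and the refitted coefficients could be compared in other ways. What stands is an omission: the aim is to show a difference, and no method for judging one is given.

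**The size depends on arm coding.** This also stands. The model term is worded as control/intervention group, and protocol 8.1 is similar. Both documents also speak of three types of recommendation versus control, which favours four levels, but the coding is not settled. Under binary coding with adjustment at *r* = 0.5, one-group-only significance (2–5%) shows no real excess over the 5% of an interaction test. The logical gap remains.

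**Missed effects are a narrow case.** Largely true. The information packs are nested, so an effect in one arm and one group only is a special pattern. The SAP also does not say whether the trigger applies per outcome. With many outcomes and time points, the chance that it opens somewhere in the trial may exceed the figures above.

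**The protocol already selected groups this way.** Only on one reading. The closing phrase of protocol 8.2 may qualify just the other variables, leaving demographic subgroups ungated. The SAP trigger would then also depart from the protocol. The wording supports either reading, so a departure cannot be asserted.

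**Bonferroni covers it.** Unclear. Protocol 8.2 plans the re-runs but names no variable, so they can be read as pre-specified or not. In any case a correction does not supply a test of the difference.

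**Conclusion.** The point holds: followed exactly, Analyses Two does not answer its own question. The trigger is an outcome association, and no test of effect modification is stated in either document.

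The size rests on the assumptions above. With equal true effects, one-group-only significance once the analysis is run ranges from 2% (binary coding, *r* = 0.5) to 35% (single contrast, unadjusted), against about 5% for an interaction test. For an effect confined to one arm and one group, the gate opens in about 27–34% against 49–60% interaction power.

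A reader might infer that these percentages are the trial's overall rate of false subgroup claims, or that the primary result is compromised. Neither follows. The percentages are conditional on running the analysis and on how results are then read, and the primary comparison does not pass through this gate. The plan should be changed here, but the matter is confined to the subgroup analysis.

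**What to change.** - Drop the main-effect trigger.
- Name the demographic variables in advance; gender and age are already in the primary model. State how arm is coded.
- For each variable, add an arm-by-variable interaction to the primary model in the full sample. Report the interaction test and the subgroup estimates with confidence intervals from that model, labelled exploratory.
- State whether the Bonferroni rule covers these tests.

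**Cost: power.** For one contrast, the interaction has standard error √(4/*h*) = 0.408 or 0.365. At 0.8 SD the ratio is 1.96 or 2.19 and power is about 49–59%; at 0.5 SD it is 23–27%. If two variables are tested at 0.025 each, the 3-df test has 38–48% power for the one-arm, one-group pattern. The SAP should say that a non-significant interaction does not show equal effects.

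**Cost: imputation.** This is more than a wording change. The SAP's imputation instructions and variable sequence show no arm variable and leave out demographics other than gender, and the SAP describes imputation as done by a blinded researcher. The 20 imputations should be re-run with arm (coded, to keep the blind), the tested variables and their products. The within-group refits as now planned need the same, because imputing without arm pulls arm differences together.
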